12.5.3 Sensitivity analysis

A sensitivity analysis for the primary endpoint will be conducted by replicating the primary endpoint analysis under each of the following:

- 1. Per-protocol population
- 2. Imputation of missing data using last-observation-carried-forward (LOCF)
- 3. Analysis stratified by study site
- 4. Analysis stratified by gender
- 5. Analysis stratified by age group

Further details of these analyses will be presented in the SAP

12.5.4 Secondary (efficacy) analysis

The secondary efficacy endpoints are derived from the primary objective and will be used to support the conclusion of the primary efficacy endpoint, provided that the primary efficacy endpoint is met. The secondary endpoints will be analysed as follows:

- 1. Change in mean sitting SBP between Visit 2 (Week 0) and Visit 4 (Week 8). Endpoint (1) will be analysed using a paired t-test with the null hypothesis that the mean change in SBP is 0 mmHg from Visit 2 to Visit 4.
- 2. Change in mean sitting DBP and SBP between Visit 3 (week4) and Visit 4 (Week 8) in patients uncontrolled at Visit 3 and up titrated to the extemporaneous combination of ZOF/AML 30/10 mg.
 - Endpoint (2) will be analysed using paired t-test for DBP and SBP with null hypotheses of 0 mmHg mean change from Visit 3 to Visit 4.
- 3. Number and proportion of patients achieving the BP goal (sitting BP≤130/80 mmHg) at Visit 2 (Week 0), Visit 3 (Week 4) and Visit 4 (Week 8).
 - Endpoint (3) will be analysed using a 95% binomial confidence interval for adherence for each visit.

MENARINI	Corporate Medical Department		
Identification Number	Version Number	State	Effective date
FORM-000050125	2.0, CURRENT	Effective	08, Jan 2021

4. Adherence to the treatments (% of doses taken/ doses to be taken) at Visit 2 (Week 0), Visit 3 (Week 4) and Visit 4 (Week 8).

Endpoint (4) will be analysed using a 95% binomial confidence interval for adherence for each visit.

In addition, all continuous efficacy variables will be summarized for all study visits using descriptive statistics for both actual values and change-from-baseline values. The Efficacy population will be used to analyse the secondary endpoints.

12.5.5 Exploratory (efficacy) analysis

The exploratory efficacy endpoints assessing change-from-baseline BP will be analysed using mixed models for repeated measured (MMRM). The models will include treatment subgroup, analysis visit, treatment subgroup-by-visit interaction, the baseline BP value as a covariate, and patient as a random effect. An unstructured covariance structure was used to model the within-patient errors. The exploratory efficacy endpoint for proportion of patients achieving controlled BP will be analysed using a logistic MMRM with similar terms.

Additional details will be summarized in the Statistical Analysis Plan.

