### 7.4 Exploratory Efficacy Analyses

Each of the exploratory efficacy analyses described in the subsections below will be performed on the following treatment subgroups:

**Test Group**: Patients who were on ZOF 30 mg or AML 5 mg at Visit 1 (Week -4) and continued the same therapies.

**Comparison Group**: Patients who switched to ZOF 30 mg or AML 5 mg from any other ACE-i or CCBs at Visit 1 (Week -4).

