### 7.4.2 Proportion of Patients (Endpoints 3.3 and 3.4)

**Endpoint 3.3**: Monotherapy: number and proportion of patients achieving the BP goal (sitting BP  $\leq 130/80$  mmHg) at Visit 2 (Week 0). Combination therapy: number and proportion of patients achieving the BP goal (sitting BP  $\leq 130/80$  mmHg) at Visit 3 (Week 4).

**Endpoint 3.4**: Monotherapy: number and proportion of patients divided in subgroup by the hypertension grade, the presence of diabetes and/or of hypercholesterolemia achieving the BP goal (sitting BP  $\leq$ 130/80 mmHg) at Visit 2 (Week 0). Combination therapy: number and proportion of patients divided in subgroup by the hypertension grade, the presence of diabetes and/or of hypercholesterolemia achieving the BP goal (sitting BP  $\leq$ 130/80 mmHg) at Visit 3 (Week 4) and Visit 4 (Week 8).

Endpoints 3.3 and 3.4 will be analyzed using a logistic MMRM to assess the proportion of patients achieving the BP goal (sitting BP  $\leq$ 130/80 mmHg). The models will be built as follows:

- Endpoint 3.3
  - *Response* = achieving BP goal (sitting BP ≤130/80 mmHg)
  - *Covariates* = treatment subgroup, study visit, treatment subgroup-by-visit interaction, baseline BP values
  - *Random effect* = patient
  - Covariance matrix = unstructured
    - In the event of lack of model convergence, other covariance structures may be used.
    - If all logistic MMRM fail to converge, this endpoint will be analyzed as described in section 7.4.2.1 below.

- Endpoint 3.4 by hypertension grade
  - *Response* = achieving BP goal (sitting BP ≤130/80 mmHg)
  - *Covariates* = treatment subgroup, study visit, treatment subgroup-by-visit interaction, baseline BP values
  - *Random effect* = patient
  - Covariance matrix = unstructured
    - In the event of lack of model convergence, other covariance structures may be used.
    - If all logistic MMRM fail to converge, this endpoint will be analyzed as described in section 7.4.2.1 below.
  - Stratification factor = Baseline hypertension grade
- Endpoint 3.4 by presence of diabetes and/or of hypercholesterolemia
  - *Response* = achieving BP goal (sitting BP ≤130/80 mmHg)
  - *Covariates* = treatment subgroup, study visit, treatment subgroup-by-visit interaction, baseline BP values
  - *Random effect* = patient
  - *Covariance matrix* = unstructured
    - In the event of lack of model convergence, other covariance structures may be used.

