    - If all logistic MMRM fail to converge, this endpoint will be analyzed as described in section 7.4.2.1 below.
  - *Stratification factor =* presence of diabetes and/or of hypercholesterolemia at baseline

The number (n), proportion (%), and 95% CI of the proportion of patients achieving controlled BP will be presented by visit and treatment subgroup. The odds ratio (OR), 95% CI of the OR, and two-sided p-value for the difference between treatment subgroups in proportion of patients achieving controlled BP will be presented where a p-value of  $\leq$  0.05 indicates a significant difference between groups.

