### 7.4.2.1 Model Nonconvergence

If the above logistic MMRMs fail to converge, endpoints 3.3 and 3.4 will be analyzed using a 95% binomial confidence interval (CI) and Odds Ratio (OR) for each visit to assess the proportion of patients, by subgroup, who achieve the BP goal. Subgroups will include those described in section 7.4, as well as subgroups for hypertension grade and the presence of diabetes and/or hypercholesterolemia.

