[2] A separate model is used for the monotherapy and combined therapy analyses. Models use an unstructured covariance matrix; achieving sitting BP goal as the response variable; visit, treatment subgroup, visit\*treatment subgroup interaction, and screening (monotherapy) or baseline (combined therapy) SBP/DBP as covariates; and a random effect for patient.

[3] A patient is considered to have met the Blood Pressure (BP) goal (controlled BP) if their SBP  $\leq$  130 mmHg AND their DBP  $\leq$  80 mmHg.

[4] n = number of patients who have achieved sitting BP goal at that visit. N = number of patients with data at that visit, regardless of BP goal status.

[5] ZOF/AML subgroup: Patients who were on ZOF 30 mg or AML 5 mg at Visit 1 (Week -4) and continued on same therapies.

[6] ACE-i/CCB subgroup: Patients who switched to ZOF 30 mg or AML 5 mg from any other ACE-I or CCBs at Visit 1 (Week -4).

Source: Listing 16.2.6

Program Name: XXXX.SAS

Programming Note:

• If a different covariance structure is used in case of model nonconvergence, footnote 2 should be updated accordingly.

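### The BP-goal models put a random patient effect into a one-record Visit 2 model, and give Visit 3/4 odds ratios that are not the contrast of the proportions printed above them

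*Protocol*

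**What the plan says.** For BP change, Protocol 12.5.5 states: "The models will include treatment subgroup, analysis visit, treatment subgroup-by-visit interaction, the baseline BP value as a covariate, and patient as a random effect". For the BP goal it adds: "The exploratory efficacy endpoint for proportion of patients achieving controlled BP will be analysed using a logistic MMRM with similar terms".

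SAP 7.4.2 carries this out for Endpoint 3.3 and both versions of Endpoint 3.4. Each model has subgroup, visit, their interaction and baseline BP, with patient as the random effect and "Covariance matrix = unstructured". It does not say whether that matrix belongs to the random effects or the residuals. The footnotes to Tables 14.2.4.3, 14.2.4.4.1 and 14.2.4.4.2 add that the monotherapy analysis (Visit 2) and the combined-therapy analysis (Visits 3 and 4) are modelled separately, each with the listed covariates "and a random effect for patient".

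SAP 7.4.2 then promises an odds ratio, its confidence interval and a "two-sided p-value for the difference between treatment subgroups in proportion of patients achieving controlled BP". The shells print observed n/N with its interval at each visit and the odds ratio directly below.

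The contrast is between patients who switched at Visit 1 and this group: "Patients who were on ZOF 30 mg or AML 5 mg at Visit 1 (Week -4) and continued the same therapies". Membership is fixed at Visit 1 and is not randomised.

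If every covariance structure tried fails to converge, SAP 7.4.2.1 says Endpoints 3.3 and 3.4 "will be analyzed using a 95% binomial confidence interval (CI) and Odds Ratio (OR) for each visit". It names no covariates and no patient effect.

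**The concern.** Three things do not fit together.

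- **Visit 2.** A patient effect separates variation between patients from variation within a patient. With one yes/no value per patient there is nothing to separate, so the odds ratio depends on a variance that the data cannot supply.
- **Visits 3 and 4.** The SAP describes the odds ratio as the subgroup difference in the proportion at goal. A logistic model with a random patient effect estimates an odds ratio at a given patient effect and baseline BP, which is a different number from the contrast of the two printed proportions. No label says so.
- **Fallback.** On non-convergence the same cell holds a crude odds ratio. The shell notes ask for a footnote change only when the covariance structure changes.

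At stake is the reading of three exploratory tables. A reader would take each odds ratio as the contrast of the n/N above it, and would compare odds ratios across tables or strata that may have come from different methods.

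**Working it through.** The plan gives no goal rate, between-patient SD or odds ratio for these endpoints, so there is no figure to reproduce. Every rate, SD and correlation below is an assumption.

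**Step 1: Visit 2, one record per patient.** Assume 108 patients per subgroup (216/2, for scale only) with 32/108 and 43/108 at goal, about 30% and 40%. With subgroup as the only term, the probability at goal is

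p = ∫ expit(η + σz) φ(z) dz.

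For any patient SD σ, an η can be found that gives exactly the observed p in each group. The fit is therefore the same at every σ, but the odds ratio exp(η₁ − η₀) is not:

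| σ | log-likelihood | odds ratio |
|---|---|---|
| 0 | −138.234 | 1.57 |
| 1 | −138.234 | 1.72 |
| 2 | −138.234 | 2.08 |
| 3 | −138.234 | 2.62 |

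The σ = 0 row is the ordinary odds ratio, (43/65)/(32/76) = 1.57.

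Adding a BP covariate leaves only the shape of the link function to inform σ. In 150 simulated Visit 2 fits with such a covariate, the estimated SD ran from about 0 to the upper bound allowed, and the odds ratio was inflated more than threefold in about a quarter of fits. That share depends on the simulation settings and on the bound. Visit and its interaction with subgroup are also empty terms in a one-visit model.

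**Step 2: Visits 3 and 4, conditional against population-averaged within the same model.** Assume 30% v 40%. The population odds ratio is (0.4/0.6)/(0.3/0.7) = 1.56. Convert a latent correlation ρ to an SD by σ² = [ρ/(1 − ρ)] × π²/3, then solve the integral above for each η. Worked case, ρ = 0.5: σ = 1.81, η₀ = −1.309, η₁ = −0.631, so the odds ratio is exp(0.678) = 1.97.

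| ρ | conditional odds ratio |
|---|---|
| 0.1 | 1.61 |
| 0.3 | 1.75 |
| 0.4 | 1.84 |
| 0.5 | 1.97 |
| 0.6 | 2.15 |
| 0.7 | 2.43 |

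On the log scale the excess over 1.56 is 27% at ρ = 0.3 and about 100% at ρ = 0.7. With no subgroup effect both odds ratios are 1.00 at every σ.

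**Step 3: the model odds ratio against the crude one.** The model adjusts for baseline BP and the printed n/N does not. Simulated trials (216 patients, two visits, true conditional odds ratio 1.5, 60 runs per setting) gave these Visit 4 medians:

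| σ | continuers' baseline BP | model odds ratio | crude odds ratio |
|---|---|---|---|
| 1 | 0.5 SD lower | 1.44 | 1.76 |
| 1 | equal | 1.66 | 1.42 |
| 1 | 0.5 SD higher | 1.60 | 1.02 |
| 2 | 0.5 SD lower | 1.58 | 1.63 |

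With 60 runs the medians are noisy, but the ordering plainly reverses. At σ = 1 with continuers 0.5 SD higher, the adjusted model without a patient effect gave 1.52 against 1.02 crude, so the covariate alone can open the gap.

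**Step 4: the fallback.** The planned odds ratio is conditional on the patient effect and baseline BP. The fallback odds ratio is conditional on neither. Steps 2 and 3 show how far apart these can be.

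**The case against.** The strongest reply is that a conditional odds ratio is a legitimate estimand, that the footnotes disclose the patient effect, that raw n/N is printed alongside, and that the null is unchanged. For Visits 3 and 4 this is fair. What remains is that SAP 7.4.2 describes the number as a difference in proportions, which it is not.

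A second reply is that the text is ambiguous. Protocol 12.5.5 ties the unstructured matrix to within-patient errors, and a residual-side fit without a random effect would give a population-averaged odds ratio. This also stands, which is why the Visit 3/4 point is conditional on the random effect being fitted as such.

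A third is that the correlation may be low, since patients uncontrolled at Visit 3 are up-titrated. At ρ = 0.1 the gap is only 1.61 against 1.56.

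Two stronger readings are tempting. A reader might infer that the odds ratio is a within-patient quantity. It is not: subgroup is fixed at Visit 1, so it compares different patients who share the same patient effect and baseline BP. A reader might also infer that it must exaggerate the difference shown by the proportions. Conditional lies further from 1 than marginal only within one model. Against crude proportions in non-randomised groups, Step 3 shows either order.

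None of these replies helps the Visit 2 model.

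**Conclusion.** The Visit 2 point holds whatever the assumptions: with one binary record per patient the patient variance is essentially unidentifiable, so the Visit 2 odds ratio in all three tables is arbitrary if a random effect is fitted. The same would apply to combination therapy in Endpoint 3.3 if it were modelled at Visit 3 alone, as SAP 7.4.2 lists it; Table 14.2.4.3 adds Visit 4.

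For Visits 3 and 4 the finding is one of mismatch, not of bias in a known direction. The gap between the conditional and population-averaged odds ratios of the same model ranges from negligible to large (1.61 to 2.43 against 1.56) under assumed rates of 30% v 40% and correlation 0.1 to 0.7. The documents do not support a claim that the printed odds ratio systematically overstates the subgroup difference.

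The switch of effect measure on non-convergence is real and unlabelled. The endpoints are exploratory and drive no trial decision, so this is a desirable improvement rather than a necessary one.

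**What to change.** 1. **Visit 2:** use ordinary logistic regression with subgroup and screening BP, without the patient effect, visit or interaction. Name screening BP in SAP 7.4.2 as the shells do. The SAP lists baseline BP, which under SAP 5.2.1 is the Visit 2 reading that determines the outcome.
2. **Visits 3 and 4:** say whether the unstructured matrix is on the random-effect or residual side. Report a risk difference or marginal odds ratio with 95% CI, standardised over baseline BP and integrated over any random effect.
3. **Fallback in SAP 7.4.2.1:** use a per-visit logistic regression adjusted for baseline BP (screening BP at Visit 2), standardised in the same way.
4. **Shells:** footnote the effect measure and the method actually used, table by table.

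The cost is SAP and footnote wording and a few lines of code, including a delta-method or bootstrap interval. Replacing the mixed model with GEE would be simpler but is a trade-off: Grade 3 BP at Visit 3 leads to withdrawal, so Visit 4 missingness depends by design on Visit 3 BP. Integrating over the random effect keeps the missing-at-random handling. The per-visit fallback does not, and its footnote should say so.

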12.5.6 Subgroup analysis

Further subgroups analyses besides those described in the exploratory endpoints will be defined in the Statistical Analysis Plan.

12.5.7 Safety analysis

Safety and tolerability of the monotherapies (ZOF 30 mg and AML 5 mg) and of the extemporaneous combination (ZOF 30 mg and AML 5 mg or AML 10 mg) will be evaluated using the Safety population. The variables for this safety endpoint are laboratory tests, physical examination, vital signs, 12-lead ECG, and incidence of AEs and SAEs.

12.5.8 *Interim analysis and stopping rules*

There will be no interim analyses for this study.

12.5.9 Data imputations

Missing BP values that occur after baseline will be imputed for the sensitivity analysis using LOCF (see 12.5.3). Any missing data for BP at baseline will not be imputed. No other standard Pag. 65 a 91

MENARINI	Corporate Medical Department		
Identification Number	Version Number	State	Effective date
FORM-000050125	2.0, CURRENT	Effective	08, Jan 2021

Sponsor: Menarini International Operations Luxembourg SA Study Code: MEIN/20/ZoAm-Hyp/001	Protocol Version 1.0 of 1	23/04/2021

imputations of missing efficacy data will be applied unless it is described later in the SAP in the respective data section.

12.6 Protocol Deviations and Protocol Amendments

No deviations from the Protocol should be initiated without prior approval by EC/HA of a Protocol Amendment according to applicable Regulations, except in case of emergency or when the change involves only logistical or administrative aspects of the trial.

Any deviation from the Protocol, SOPs, GCP and applicable Regulatory Requirements should be immediately reported to the Sponsor.

Changes in the study protocol will require a protocol amendment. Such amendments will be agreed upon and approved in writing by all signatories of the protocol.

If amendments are substantial, i.e. are likely to have an impact on the safety of the subjects, or to change the interpretation of the scientific documents in support of the conduct of the study, or if they are otherwise significant, the ECs and the CAs in the participating countries have to approve these amendments before implementation, according to applicable Regulatory Requirements.

Changes which have no significant impact on medical or scientific validity of the study will be agreed upon and approved in writing by all signatories of the protocol and the EC will be notified of this protocol amendment.

Any substantial amendments of the protocol will be integrated in an updated study protocol. The Principal Investigator must ensure full compliance with the updated study protocol.

12.7 End of Study Visit

The final subject last visit that occurs on Week 8 ± 2 days will be considered to be end of study.

12.8 Statistical Analysis Plan

The statistical analysis plan (SAP) will be finalized before the study. The SAP will describe in detail study endpoints and statistical analyses, including the analysis of the primary as well as additional endpoints. In case changes of the original primary endpoint or of the original primary analyses will occur during the study, these changes will be the subject of a substantial protocol amendment.

All statistical analyses not pre-specified and run after additional/exploratory analyses.

MENARINI	Corporate Medical Department		
Identification Number	Version Number	State	Effective date
FORM-000050125	2.0, CURRENT	Effective	08, Jan 2021

Sponsor: Menarini International Operations Luxembourg SA Pr

Protocol Version 1.0 of 1 23/04/2021

Study Code: MEIN/20/ZoAm-Hyp/001

13 STUDY DISCONTINUATION AND CLOSURE

Menarini International Operations may discontinue this study prematurely for reasonable cause. Possible reasons for early termination or temporary suspension of the study include, but is not limited to:

- Study closure based on PI decision and/or
- Study closure based on Sponsor decision and/or
- Study closure based on Regulatory or other oversight bodies initiation and/or
- Review of serious, unexpected, and related AEs and/or
- Non-compliance.

In case this study was temporarily suspended or prematurely terminated, written notification documenting the reason for study suspension or termination will be provided by the suspending or terminating party at a reasonable time in advance of the intended termination.

The Investigator may also discontinue this study at his/her site for reasonable cause after notifying the IEC and providing written notice to Menarini International Operations at a reasonable time in advance of the intended termination.

Please note advanced notice is not required by either party if the study is stopped due to safety concerns.

Menarini International Operations and the Investigator should take the following steps to follow up on patient safety and ensure data integrity:

- Immediately notify the pharmacovigilance officer at Biorasi
- Notify the IEC within 24 hours
- Contact all patients by phone and distribute written communication that the study has been stopped
- Advise all patients to report for an early termination visit
- Make plans to follow all patients for AEs for two months after the study has been stopped or for as long as it takes for any AE/SAEs to resolve, whichever is longer
- Instruct study staff to enter all data in the case report form and ensure their completion

MENARINI	Corporate Medical Department		
Identification Number	Version Number	State	Effective date
FORM-000050125	2.0, CURRENT	Effective	08, Jan 2021

14 DIRECT ACCESS TO SOURCE DATA / DOCUMENTS

The Investigator and/or Institution will permit trial related monitoring, audits, EC review, and regulatory inspections, providing direct access to source data/documents upon request.

15 QUALITY CONTROL AND QUALITY ASSURANCE

15.1 Study Monitoring / Data Quality Control

Site monitoring is conducted to ensure that the rights and well-being of trial subjects are protected, that the reported trial data are accurate, complete, and verifiable, and that the conduct of the trial is in compliance with the currently approved protocol / amendment(s), with ICH GCP, and with applicable regulatory requirement(s).

The monitoring of the conduct of the study and progress of the clinical investigation will proceed in accordance to the Monitoring Plan. The purpose of the Monitoring Plan is to establish guidelines for managing, monitoring, and working with Investigational Sites for this study.

The Monitoring Plan provides information that will be used by Clinical Research Associates (CRAs) to ensure the quality of the data including the type, frequency, and extent of monitoring, who will be provided reports of monitoring and whether independent audits of the monitoring activities will be conducted. The Monitoring Plan also provides detailed information about the number of study sites, Site Initiation Visits (SIVs), Study Site Visits (SSVs), Interim monitoring visits (IMVs), and close-out visits.

The Investigator will be contacted by the study monitor on a regular basis. The monitor will have the responsibility of reviewing the ongoing study with the Investigator to verify adherence to the protocol and to deal with any problems.

Quality checks that will be performed on trial documents and on the collected data include, but is not limited to, ICF review and source data verification. Detailed information can be found in the Monitoring Plan.

MENARINI	Corporate Medical Department		
Identification Number	Version Number	State	Effective date
FORM-000050125	2.0, CURRENT	Effective	08, Jan 2021

The Investigator agrees to allow access to all study materials needed for the proper review of study conduct. The Investigator agrees to assist the monitor in resolving any problem that may be detected during the monitoring visit or data cleaning process.

